#### 2.0 BACKGROUND

2.1 Von Hippel Lindau Syndrome

The VHL syndrome affects approximately 1 in 35000 live births each year worldwide. The disease results from an autosomal-dominant mutation associated with deletion of the *VHL* gene located on the short arm of chromosome 3. The VHL protein is directly responsible for downregulating hypoxia-inducible factor alpha (HIF) transcription factors responsible for several angiogenic responses to hypoxia. Thus, mutations of the VHL gene lead to the regulatory loss of HIF, with increased intracellular HIF during normoxia being the primary common pathway leading to the downstream manifestations of the syndrome via induction of VEGF, PDGF, erythropoietin, and a variety of other angiogenic pathways. The clinical presentation of this syndrome is characterized in late childhood and early adulthood by hemangioblastomas of the brain, spine, and retina, in addition to renal cell carcinoma, pheochromocytoma, neuroendocrine tumors of the pancreas, other benign tumors (e.g., endolymphatic sac tumors) as well as cystic lesions in various organs such as the kidneys and pancreas. Renal cell carcinomas and hemangioblastomas are directly related to HIF pathway activation, while pheochromocytomas appear to be induced via non-HIF pathways. The multi-organ morbidity of these lesions as well as their treatment is significant in these patients, who must often endure repeated, serial interventions of the CNS, eye, kidneys, pancreas, adrenal, and other organs. While little data has been published in regard to the multiplicity of interventions for all the involved organ systems, one report has shown that by age 30, most patients with VHL have had greater than 2 interventions for any involved organ. Of those with RCC, 88% required intervention at an average range of 1.4 to 3 interventions per year. Renal and CNS tumors comprise the majority of those causing

Protocol 2011-0465 ASeptember 6, 2017 Page 6 of 50

the greatest impact, as does their treatment.

Genetic characterization of the various mutations has been classified as Type 1 (no pheochromocytoma) and Type 2 (presence of pheochromocytoma) which is further characterized into 2a, low risk of renal cancer, 2b, high risk of renal cancer; and 2c, pheochromocytoma only.

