## **3.0 PATIENT SELECTION**

- 3.1 Inclusion Criteria
  - 1. Subjects must provide written informed consent prior to performance of study-specific procedures or assessments, and must be willing to comply with treatment and follow-up. Procedures conducted as part of the subject's routine clinical management (e.g., blood count, imaging study) and obtained prior to signing of informed consent may be utilized for screening or baseline purposes provided these procedures are conducted as specified in the protocol.
  - 2. Eastern Cooperative Oncology Group (ECOG) performance status of  $\leq 2$ .
  - 3. Genetically confirmed diagnosis of VHL or measurable disease consistent with the clinical diagnosis of VHL. (Please refer to criterion #5)

Protocol 2011-0465 ASeptember 6, 2017 Page 14 of 50

- 4. Measurable disease criteria:
  - At least one measurable VHL related lesion, which is undergoing surveillance, and patient is not at immediate risk of needing intervention for this or other lesions. Biopsy is not required given the known likely etiology and natural history in the setting of a positive genetic test.
    - a. Brain: asymptomatic hemangioblastoma,  $\geq 0.5$  cm
    - b. Spine: asymptomatic hemangioblastoma,  $\geq 0.5$  cm
    - c. Renal: solid mass suspicious for RCC ≥1 cm or cystic mass (Bosniak 3-4) ≥1 cm.
    - d. Pancreas: solid mass  $\geq 1$  cm and  $\leq 3$  cm suspicious for neuroendocrine tumor, or neuroendocrine tumor > 3 cm but not considered operable.
    - e. Eye: asymptomatic peripapillary and/or macular hemangioblastoma, any size
    - f. Adrenal: asymptomatic or controlled pheochromocytoma greater than 1cm in size
- 5. Patients may have received prior VHL-related systemic therapy, provided not within 14 days or five half-lives of a drug (whichever is longer) prior to the first dose of pazopanib.

Protocol 2011-0465 ASeptember 6, 2017 Page 15 of 50

6. Adequate organ-system function as defined in Table 4.

System	Laboratory Values
Hematologic	
Absolute neutrophil count	$\geq 1.5 \text{ X } 10^{9}/\text{L}$
(ANC)	
Hemoglobin a	$\geq 9 \text{ g/dL} (5.6 \text{ mmol/L})$
Platelets	≥100 X 10  /L
Prothrombin time (PT) or	≤1.2 X ULN
international normalized ratio (INR) b	
Activated partial thromboplastin	≤1.2 X ULN
time (aPTT)	
Hepatic	
Total bilirubin	≤1.5 X ULN
Alanine amino transferase	≤2.0 X ULN
(ALT) and Aspartate	
aminotransferase (AST) c	
Renal	

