### 11.1.3 Target lesions

All measurable lesions up to a maximum of five lesions per organ and 10 lesions in total, representative of all involved organs, should be identified as target lesions and recorded and measured at baseline. Target lesions should be selected on the basis of their size (lesions with the longest diameter) and their suitability for accurate repeated measurements (either by imaging techniques or clinically). A sum of the longest diameter (LD) for all target lesions will be calculated and reported as the baseline sum LD. The baseline sum LD (per target organ as per Section 11.1.5) will be used as reference by which to characterize the objective tumor response.

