### 11.1.4 Non-target lesions

All other lesions (or sites of disease) should be identified as non-target lesions and should also be recorded at baseline. Non-target lesions include measurable lesions that exceed the maximum numbers per organ or total of all involved organs as well as non-measurable lesions. Measurements of these lesions are not required, but the presence or absence of each should be noted throughout follow-up.

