### 11.1.5 Rationale for Modification to RECIST Criteria

Patients with VHL have a germline genetic mutation, which displays differential organ phenotypes. Due to the same mechanisms, it is reasonable to assume that responses to targeted therapy may be different in various organ-sites as a result of epigenetic, environmental, and circulatory differences. Using strict RECIST criteria (such as using the sum of all lesions) will lead to potentially significant loss of

Protocol 2011-0465 ASeptember 6, 2017 Page 44 of 50

important information. For the purposes of this study, imaging-based measurements will follow RECIST criteria except for the following conditions:

- Target organ systems will be uncoupled and evaluated separately. Summation of lesion size will be performed separately for the kidney, pancreas, CNS (brain+spine), and retina, and changes from baseline compared using these measurements.
- The number of lesions measured from each site will be modified (specified in Section 11.2, Guidelines for Evaluation of Measurable Disease), as there may be innumerable lesions present, some probably too small to give reproducible and accurate measurements.
- 11.2 Guidelines for Evaluation of Measurable Disease

All measurements should be taken and recorded in metric notation using a ruler or calipers. All baseline evaluations should be performed as closely as possible to the beginning of treatment and not more than 6 weeks before the beginning of the treatment.

The same method of assessment and the same technique should be used to characterize each identified and reported lesion at baseline and during follow-up. Imaging-based evaluation is preferred to evaluation by clinical examination when both methods have been used to assess the antitumor effect of a treatment.

- CT scans: spiral, multiphasic, contrast-enhanced computed tomography of abdomen and pelvis with thin-cuts (5 mm) of adrenals, kidneys, and pancreas. Multi-channel helical CT scan only will be used, as this will provide the most reproducible and reliable size measurements, particularly for lesions in the range of 1 cm.
- CT Interpretation: all CT studies will be evaluated by a radiologist according to standard practice. Up to 5 of the largest renal lesions and 3 of the largest pancreatic lesions will be measured in the single longest dimension per RECIST guidelines.

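### Sections 11.1.3 and 11.2 do not carry criterion 4's limit on renal and pancreatic lesion type into target selection, so simple cysts can enter the organ sum that decides PR and PD

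*Combined protocol and SAP*

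**What the plan says.** **Entry.** Section 3.1, criterion 4, asks for "At least one measurable VHL related lesion, which is undergoing surveillance" at any of six sites. For the kidney the lesion must be a "solid mass suspicious for RCC ≥1 cm or cystic mass (Bosniak 3-4) ≥1 cm". For the pancreas it must be a solid mass of 1 to 3 cm "suspicious for neuroendocrine tumor, or neuroendocrine tumor > 3 cm but not considered operable". A simple renal cyst or a pancreatic cyst does not qualify.

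**Target selection.** Section 11.1.1 defines measurable lesions outside the CNS by size alone: 20 mm with conventional techniques, 10 mm with spiral CT. The list of non-measurable disease in Section 11.1.2 does not name cysts. Section 11.1.3 then states: "Target lesions should be selected on the basis of their size (lesions with the longest diameter) and their suitability for accurate repeated measurements". Section 11.2 sets the numbers: "Up to 5 of the largest renal lesions and 3 of the largest pancreatic lesions will be measured in the single longest dimension". None of these sections names a tissue type or requires the lesion that qualified the patient to be a target. For lesions beyond the caps, Section 11.1.4 says: "Measurements of these lesions are not required, but the presence or absence of each should be noted throughout follow-up".

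**Scoring.** Under Section 11.1.5 diameters are summed separately for kidney, pancreas, CNS and retina. Section 11.3.1 reads PR (a fall of at least 30%) and PD (a rise of at least 20%, or a new lesion) from that sum. Section 12.1 takes CR+PR at 24 weeks as the efficacy endpoint and monitors PD with a stopping rule.

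**Background.** Section 2.1 names "cystic lesions in various organs such as the kidneys and pancreas" as part of the syndrome. Table 1 in Section 2.3.1, on the earlier sunitinib study, reports RECIST best response for 9 renal cysts and 3 pancreatic cysts, in rows separate from renal cell carcinoma (RCC) and pancreatic neuroendocrine tumor (NET).

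**The concern.** The lesions that bring a patient in through the kidney or pancreas and the lesions that decide response there are defined by different rules. In a syndrome that includes cysts in both organs, a size ranking with no tissue condition can put cysts and tumor into one sum. If the cysts do not shrink, a real tumor response can be recorded as SD. If they do not grow, real tumor growth can be recorded as something less than PD. The first touches the efficacy endpoint and the second touches the PD stopping rule. Two radiologists could also read the same scan differently, since one may leave cysts out and the other may include them. The earlier study scored cysts by RECIST, so their exclusion here cannot be taken for granted. There they had their own rows; here they would share a sum with the tumor.

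**Working it through.** **The plan's own figure.** Section 12.1 gives a maximum standard error of 0.08 with 40 patients. √(0.25/40) = 0.079, which agrees. The point below concerns what is counted as a response, not this precision.

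**Inputs.** PR threshold 30% and PD threshold 20% of the organ sum (Section 11.3.1). Mean baseline size 2.41 cm for RCC and 1.89 cm for NET (Table 2, Section 2.3.1), used as illustrative tumor diameters. Smallest cyst measurable on spiral CT: 1 cm (Section 11.1.1). Cyst sizes per patient are not given, so X is left free.

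**Formulas.** Let T be the tumor diameter (or the sum over tumors) and X the sum of unchanged cyst diameters in the same organ.
- If the tumor shrinks by a fraction s, the organ sum falls by sT/(T+X). PR therefore needs s ≥ 0.30 × (T+X)/T.
- If the tumor grows from a baseline that is also the smallest sum, PD from its growth alone needs g ≥ 0.20 × (T+X)/T.
- PR becomes impossible when T/(T+X) < 0.30, that is, when X > (7/3)T.

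| X relative to T | Tumor shrinkage needed for PR | Tumor growth needed for PD |
|---|---|---|
| 0 | 30% | 20% |
| 0.5T | 45% | 30% |
| T | 60% | 40% |
| 2T | 90% | 60% |
| 2.33T | 100% | 66.7% |

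**One small cyst.** With T = 2.41 cm, X = 1 cm and s = 40%: 0.40 × 2.41/3.41 = 28.3%, which is SD. The break-even for a 40% shrinkage is X = 0.40 × 2.41/0.30 − 2.41 = 0.80 cm. Any unchanged cyst large enough to be measurable on spiral CT exceeds that.

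**Upper limits.** PR is impossible above X = (7/3) × 2.41 = 5.62 cm beside the RCC, and above (7/3) × 1.89 = 4.41 cm beside the NET, even if the tumor disappears.

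**Several tumors.** Dilution weakens as tumor diameter in the sum grows. With three tumors of 2.41 cm (T = 7.23 cm) and one 1 cm cyst, PR needs 0.30 × 8.23/7.23 = 34.1%.

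**Displacement.** Five renal cysts larger than the tumor, or three larger pancreatic cysts, would fill the cap. The tumor would then be non-target, and the non-target categories in Section 11.3.2 contain no PR.

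**Illustration of the effect on the rate.** The earlier study saw PR in 6 of 18 RCC lesions (33%). If cysts masked 25% of RCC responders, the observed rate would be 0.333 × 0.75 = 25%; if they masked 50%, it would be 0.333 × 0.50 = 17%. Both shares are assumptions.

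**The case against.** The strongest reply is that the protocol, read as a whole, already points to tumors. Section 11.1 speaks of tumor lesions. Section 11.1.3 requires suitability for repeated measurement as well as size. Criterion 4 is itself headed as the criteria for measurable disease. Section 11.1.5 otherwise keeps RECIST, whose text is not part of the documents. This stands in part: a reader has grounds to leave simple cysts out, and it would be wrong to say that Section 11 selects the largest lesions of any kind. But none of these places excludes cysts. Section 11.1.1 gives its own size-only definition of measurable, and a well-defined cyst can be suitable for repeated measurement.

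Four stronger readings are tempting and are not supported.
- **That entry as a whole requires a solid mass.** It does so only through the kidney or pancreas; brain, spine, eye and adrenal lesions also qualify. A patient who enters by one of those routes could have a renal sum made up only of cysts.
- **That the response rate is known to be biased down to 25% or 17%.** No cyst burden is given. The absence of PR in 9 renal and 3 pancreatic cysts is thin, lesion-level evidence on another drug: the exact 95% upper limits are 34% and 71%.
- **That growing cysts will trip the stopping rule.** This is possible in principle, but all 12 cysts in Table 1 were stable.
- **That the tumor will be displaced.** This needs five or three larger cysts in one patient, while Table 1 lists 9 renal and 3 pancreatic cysts in all. It is the extreme case. Dilution needs only one cyst.

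It can also be said that diluted shrinkage understates efficacy, which is the cautious direction in a single-arm trial. That is true for response. It is not true for PD, where dilution hides tumor growth from a rule meant to stop the trial.

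**Conclusion.** The concern holds as a gap in the definition of target lesions, and should be fixed. The rule as written lets simple cysts share an organ sum with the qualifying tumor. Where that happens and the cysts do not change, the tumor shrinkage needed for PR and the growth needed for PD are both multiplied by (T+X)/T. One unchanged 1 cm cyst beside a 2.41 cm RCC is enough to turn a 40% tumor shrinkage into SD.

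The size for a single patient is exact arithmetic, given unchanged cysts. The size for the trial is unknown, because the documents state neither cyst sizes nor how common cysts are, and readers may in practice exclude them.

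The conclusion rests on two readings. Response is CR+PR as in Section 12.1; under the note in Section 11.3.3 that also counts SD, a PR read as SD would not change the rate. PD is read from the organ sum as in Section 11.3.1; if the reference in Section 12.1 to progression of any lesion means lesion by lesion, the dilution of PD would not apply. The sample size and the stopping boundaries are not in question here.

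**What to change.** In Sections 11.1.3 and 11.2:
- Limit renal and pancreatic target lesions to the types in criterion 4: solid or Bosniak 3-4 renal masses, and solid pancreatic masses or neuroendocrine tumors. Keep the caps of five and three.
- Require the lesion in those organs that qualified the patient to be a target lesion.
- Record other renal and pancreatic cysts and describe their size change separately, as Table 1 of the earlier study did, outside the organ sum used for CR, PR and PD.

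Because Section 11.3 scores any new lesion as PD, the same text should say whether a new simple cyst counts as one.

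The cost is a few sentences. Scans, readers and the number of patients stay the same. The downside is that cyst size change leaves the primary sum and is only described, and a patient whose kidney or pancreas holds only simple cysts has no target lesion in that organ.

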11.3 Response Criteria

11.3.1 Evaluation of target lesions (this will be an organ-specific evaluation, please see Section 11.1.5 *Rationale For Modified RECIST Criteria*)

Complete Response (CR):	Disappearance of all target lesions		
Partial Response (PR):	At least a 30% decrease in the sum of the longest diameter (LD) of target lesions, taking as reference the baseline sum LD		
Progressive Disease (PD):	At least a 20% increase in the sum of the LD of target lesions, taking as reference the smallest sum LD recorded since the treatment started or the appearance of one or more new lesions		
Stable Disease (SD):	Neither sufficient shrinkage to qualify for PR nor sufficient increase to qualify for PD, taking as reference the smallest sum LD since the treatment started		

11.3.2 Evaluation of non-target lesions

Complete Response (CR):	Disappearance of all non-target lesions
Incomplete Response/ Stable Disease (SD):	Persistence of one or more non-target lesion(s)
Progressive Disease (PD):	Appearance of one or more new lesions and/or unequivocal progression of existing non-target lesions

Although clear progression of "non-target" lesions only is exceptional, in such circumstances the opinion of the study chair should prevail.Note: If tumor markers are initially above the upper normal limit, they must normalize for a patient to be considered in complete clinical response.

11.3.3 Evaluation of best overall response

The best overall response is the best response recorded from the start of the treatment until disease progression/recurrence (taking as reference for progressive disease the smallest measurements recorded since the treatment started). The patient's best response assignment will depend on the

Protocol 2011-0465 ASeptember 6, 2017 Page 46 of 50

Target Organ Lesions	Non-Target Organ Lesions	New Lesions	Overall Response
CR	CR	No	CR
CR	Incomplete response/SD	No	PR
PR	Non-PD	No	PR
SD	Non-PD	No	SD
PD	Any	Yes or No	PD
Any	PD	Yes or No	PD
Any	Any	Yes	PD

achievement of both measurement and confirmation criteria.

Note:

- X For the purposes of this study, response rate (RR) is based on CR+PR+SD.
- X Patients with a global deterioration of health status requiring discontinuation of treatment without objective evidence of disease progression at that time should be classified as having "symptomatic deterioration." Every effort should be made to document the objective progression, even after discontinuation of treatment.
- X In some circumstances, it may be difficult to distinguish residual disease from normal tissue. When the evaluation of complete response depends on this determination, it is recommended that the residual lesion be investigated (fine needle aspirate/biopsy) before confirming the complete response status.

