### 9.0 CORRELATIVE/SPECIAL STUDIES

- 9.1 Correlate responders/nonresponders with genetic mutation analysis in order to define genetic signatures of responses at the organ level.
- 9.2 Baseline, week 12 and week 24 blood will be drawn and processed for cytokineangiogenesis factor analysis. A 50 panel Luminex bead based assay will be employed to evaluate baseline and therapy-induced changes in the profile. This profile will also be compared to internally generated data on patients with sporadic RCC to further explore the disease and therapy specificity of the profile.

9.3 Baseline, week 12 and week 24 blood will be drawn to evaluate baseline circulating endothelial cells and their changes as a function of therapy. These exploratory data will be employed to generate hypotheses on the interaction between host, tumor and therapy.

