12.1 Design and sample size/power

In this study, we will treat up to 40 patients with VHL who have measurable VHL related lesions. Patients will receive Pazopanib 800mg PO daily for up to 24 weeks. Patients may choose to continue the regimen beyond 24 weeks until evidence of objective disease progression. Efficacy will be determined by the RECIST overall response rate (CR+PR) at 24 weeks. Early termination due to progressive disease or toxicity will be considered as a failure. Patients not completing 1 month of therapy due to a reason other than drug toxicity or progressive disease will be considered inevaluable. We will monitor for any lesion progression (PD) and drug discontinuation due to toxicity (DD) during the whole period of the treatment simutaneously. If there is a high probability that the PD rate exceeds 20% or the DD rate exceeds 10%, the trial will be stopped early and the drug will not be considered of interest for further study. Formally, the study will be terminated if Pr(PD Rate > 0.20 | Data) > 0.90 or Pr(DD)Rate > 0.10 | Data) > 0.90. The assumed prior distributions for PD rate and DD rate are Beta (0.2, 0.8) and Beta (0.1, 0.9), respectively, with one patient's worth of information. The study will be monitored in cohorts of 10 patients. Consideration to stop the trial will be given according to the stopping boundaries in Table 1. The operating characteristics for these stopping rules are summarized in Table 2, based on 10,000 simulations. Specifically, if the PD rate is 20% and DD rate is 0.10, then there is a 27% chance to stop the trial early and the average expected number of patients

Protocol 2011-0465 ASeptember 6, 2017 Page 48 of 50

treated will be 33. On the other hand, if (PD rate, DD rate) are (0.10, 0.05), or (0.10, 0.30), then the early stopping probabilities will be 3% and 94% and the average numbers of patients treated are expected at 39 and 16, respectively. If the trial continues to the end with 40 patients treated, we will be able to estimate the response rate at 24 weeks with standard error not larger than 0.08, i.e., the half length of the 95% confidence interval will not exceed 15%.

Total Number of Patients Treated	Stop if number of Progressions >=	Stop if number of Drug Discontinuation (due to Toxicity) >=
10	4	3
20	7	5
30	10	6

Table 1. Stopping boundaries for PD and DD monitoring.

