### 12.2 Analysis Plans

If the trial is stopped early, this drug will not be considered of interest for future study VHL patients. If all 40 patients are accrued, we will estimate the response rate, early progression rate, toxicity rate and their corresponding 95% posterior credible intervals.

Biomarker endpoints and genetic mutations will be measured at baseline and/or over time. Summary statistics, including frequency tabulation, means, standard deviations, median, and range, will be used to describe subject characteristics and marker data. The chi-squared ( $\gamma^2$ ) test or Fisher's exact test will be used to test the association between two categorical variables, such as response and prognostic factors and discrete markers. The association among various continuous and discrete markers and response may be assessed first by the exploratory data analysis graphically and tested using Wilcoxon rank sum test. Correlation among continuous biomarkers will be examined by Pearson or Spearman rank correlation coefficients. Both univariate and multivariate logistic regressions may be performed to model the baseline prognostic factors such as age, gender, race, smoking history, performance status, markers, etc, on response, when appropriate. We will also use the generalized estimating equations to model correlated discrete variables. Repeated measures analysis including mixed effects model will be performed to analyze continuous biomarkers change over time. Time to progression (TTP) will be estimated using the Kaplan-Meier method. Log-rank test will be performed to test the difference in survival between prognostic groups. Regression analyses of survival data based on the Cox proportional hazards model will be

Protocol 2011-0465 ASeptember 6, 2017 Page 49 of 50

conducted on TTP. The proportional hazards assumption will be evaluated graphically and analytically, and regression diagnostics (e.g., martingale and Shoenfeld residuals) will be examined to ensure that the models are appropriate.

Table 2. Operating characteristics for the stopping rules for excessive PD rate or DD rate

True PD Rate	True DD Rate	Probability of	Average Expected #
		Early	of Patients
		Termination	
0.10	0.05	0.03	39.2
0.30	0.05	0.57	25.8
0.20	0.10	0.27	33.1
0.30	0.10	0.61	24.6
0.30	0.15	0.71	22.1
0.10	0.20	0.64	25.7
0.20	0.20	0.70	23.4
0.30	0.20	0.84	18.9
0.10	0.30	0.94	16.3

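### Section 11.3.3 counts stable disease in the study's response rate, while Section 12.1 judges efficacy by CR+PR at 24 weeks, and nothing reconciles the two

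*Combined protocol and SAP*

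**What the plan says.** Section 11.3.3 sets out how best overall response is assigned: "The best overall response is the best response recorded from the start of the treatment until disease progression/recurrence". A note under its response table then adds: "For the purposes of this study, response rate (RR) is based on CR+PR+SD".

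Section 12.1 defines the efficacy endpoint differently: "Efficacy will be determined by the RECIST overall response rate (CR+PR) at 24 weeks". It continues: "Early termination due to progressive disease or toxicity will be considered as a failure". It also gives the precision expected with 40 patients: "we will be able to estimate the response rate at 24 weeks with standard error not larger than 0.08".

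The term then recurs without its categories being named. Section 12.2 says: "If all 40 patients are accrued, we will estimate the response rate, early progression rate, toxicity rate", and plans categorical tests "to test the association between two categorical variables, such as response and prognostic factors and discrete markers". Section 9.1 says: "Correlate responders/nonresponders with genetic mutation analysis in order to define genetic signatures of responses at the organ level", and does not define a responder.

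Elsewhere the document uses response in the CR/PR sense. Section 11.0 asks for confirmatory scans for objective responses, Section 11.4.1 requires confirmation of PR and CR only, and Section 11.4.2 starts the duration of response at CR or PR. Section 11.4.3 gives stable disease a duration of its own.

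**The concern.** Both statements are current text and both claim to define response for this trial. The note in 11.3.3 is worded as study-wide, and it sits in the section that assessors use to assign response. An analyst who follows it reports a different efficacy result from one who follows 12.1.

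This matters more than it would in a comparative trial. There is no control arm and no null or target response rate, so the estimated rate, with its interval, is the efficacy finding. With two definitions in the protocol, the choice between them could be made after the data are seen.

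The two rates also mean different things. Section 2.5 acknowledges that some VHL lesions grow slowly, so stable disease over 24 weeks can occur without any drug effect. A rate that includes SD cannot be read as tumor shrinkage. The responder groups for the genotype work in 9.1 could change in the same way.

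**Working it through.** **1. The two definitions side by side**

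| | Section 11.3.3 | Section 12.1 |
|---|---|---|
| Categories counted | CR, PR, SD | CR, PR |
| Time frame | best response from start of treatment to progression (from the section that holds the note) | week 24 |
| Early termination for PD or toxicity | no rule | failure |

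Only the first row is stated in the note itself; the other two follow from where it sits. For example, a patient with SD at the week-12 scan who then stops for toxicity keeps a best response of SD and counts under 11.3.3. The same patient is a failure under 12.1.

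**2. The plan's own precision figure (12.1)**

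With n = 40, the largest standard error is sqrt(0.5 × 0.5 / 40) = 0.0791, which agrees with the stated bound of 0.08. The largest normal-approximation 95% half-length is 1.96 × 0.0791 = 0.155. The stated 15% is met by a credible interval with a uniform prior (largest half-length 0.149). The bound is worst case over all rates, so it holds whichever definition is used.

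**3. Stopping rules (12.1)**

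The boundaries of 4/7/10 progressions and 3/5/6 toxicity discontinuations at 10/20/30 patients reproduce from the Beta(0.2, 0.8) and Beta(0.1, 0.9) priors with the 0.90 cutoff. They contain no response term, so the conflict does not reach them.

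**4. Gap between the definitions, per patient**

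Take 40 evaluable patients with one response status each. Let B be the number with SD at week 24.

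- Read at week 24: (CR+PR+SD) − (CR+PR) = B/40. Each SD patient adds 1/40 = 2.5 points.
- Read as best response: provided no patient with CR, PR or SD at week 24 had an earlier PD, all of them have a best response of at least SD. The gap is then at least B/40. Patients with SD, PR or CR before a later PD or toxicity stop add to it.

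The documents give no patient-level SD rate, so B is assumed:

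- B = 4: 4/40 = 10 points
- B = 7: 7/40 = 17.5 points
- B = 24: 24/40 = 60 points

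Worked example: 8 patients with CR or PR and 7 with SD give 8/40 = 20.0% under 12.1. Counting SD gives 15/40 = 37.5%.

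As a yardstick only, B = 6 gives 15.0 points, just under the largest normal-approximation half-length of 15.5, and B = 7 exceeds it.

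**5. Lesion-level illustration (Section 2.3.1, Table 1, sunitinib)**

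- Renal cell carcinoma: CR+PR 6/18 = 33.3%; with SD 16/18 = 88.9%
- Hemangioblastoma: 0/21 = 0%; with SD 19/21 = 90.5%
- All lesions: 6/63 = 9.5%; with SD 59/63 = 93.7%

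Counts are used because the printed renal percentages do not match them (10/18 = 56%, printed as 67). These are best responses of individual lesions to another drug. They show how far the definition can move a rate and do not forecast this trial.

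**The case against.** The strongest reply is that 12.1 plainly governs. It is the only sentence that says how efficacy is determined, 12.2 most naturally inherits its definition, and Sections 11.0, 11.4.1 and 11.4.2 all use response in the CR/PR sense. Section 12.1 also speaks of a RECIST overall response rate, while the note speaks of a response rate, so two separate measures may have been intended. No decision threshold uses the rate. On this view, little is at risk.

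Those points make the note the outlier but do not remove it. It presents itself as a deliberate choice for this study, and no text labels it as a second measure. The two-measure reading is weakened because 12.1 itself goes on to refer simply to the response rate at 24 weeks.

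Some of the other side's case does stand:

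- Support for a deliberate choice exists. Section 2.5 doubts that RECIST suits slow-growing lesions, and Section 7.4 treats stabilization as benefit. The sponsor should confirm which measure was meant as primary.
- The undefined responder in 9.1 is partly a gap of its own and is a secondary point here.
- The step of 2.5 points assumes all 40 patients are in the denominator. Section 12.1 allows some to be inevaluable, and each patient then counts for slightly more.
- Section 11.1.5 evaluates organs separately, and no rule combines them into one status per patient. That question is separate and stays open.
- The gap is a fixed difference within the same patients, not sampling error, so comparing it with a confidence half-length conveys scale and nothing more.

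**Conclusion.** The contradiction is real and must be corrected before analysis. Sections 11.3.3 and 12.1 give incompatible response rates for the main efficacy estimate of an estimation-only trial.

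The size depends on how many patients have stable disease, which the documents do not give. The range of 10 to 60 points rests on an assumed 4 to 24 SD patients, 40 evaluable patients and one response status per patient. Under the best-response reading, the same figures are minimums, subject to the no-earlier-PD condition above. The harm is to the reported efficacy result and its interpretation, and secondarily to the responder analyses. The sample size, stopping rules and precision statement are sound on this point.

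**What to change.** 1. In 11.3.3, replace the note with wording such as: *Response rate = CR+PR, as in Section 12.1; CR+PR+SD is reported separately as the disease control rate, at 24 weeks and as best overall response, each labelled.*
2. In 12.2, state that the response rate to be estimated, and the response outcome in the association analyses, is CR+PR at 24 weeks as defined in 12.1.
3. In 9.1, define a responder by the same CR+PR criterion, applied per organ.

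CR+PR is proposed because 12.1 names it for efficacy and the confirmation and duration rules fit it. The confirmation rules in 11.0, 11.3.3 and 11.4.1 are left as they are. Whether a PR first seen at week 24 needs its later confirmation to count, and how organs combine into a patient-level status, are separate questions that this change does not settle.

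The cost is protocol wording only: no added patients or scans and no change to the stopping rules. No information is lost, because CR+PR+SD is still reported under its own name.
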